5.1. Study design

Propensity score matched comparative cohort studies with two-stage meta-analysis.

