5.6. Statistical analysis**5.6.1. Brief summary of the analysis method (for publication)**

For the primary analysis, propensity scores will be used to match new users of the target exposure (DOAC) to new users of the comparator exposure (VKAs), to control for confounding. For the secondary analysis, propensity scores will be used to match new users of the individual target exposures to the comparator exposure (VKAs). For all analyses, cause-specific Cox proportional hazards models will be used to estimate the relative hazard ratio of ILD after exposure. Finally, meta-analysis methods will be used to synthesise results across databases.

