5.6.2. Main statistical methods

Propensity score matching will be performed using a 1:1 matching of warfarin users to DOAC users using a caliper width of 0.2 of the standard deviation of the logit of the propensity score. [11] We will include the baseline risk factors and calendar year as predictor variables in the propensity score. Matching will occur by indication (AF and VTE). Absolute standardised mean differences (SMD) for each variable will be calculated before and after propensity score matching, with SMD of less than 0.1 representing successful matching. We will visually check the distributions of the propensity scores across treatment arms, within strata (indication, database). If the sample size appears insufficient after matching, we will use Inverse Probability Treatment Weighting (IPTW) instead of matching.

In the propensity-matched cohort, the incidence of each study outcome will be estimated between target (DOAC) and comparator (warfarin) groups. Cox models will be used to calculate hazard ratios for the instantaneous risk of the ILD outcome. Where death is available in the data source, competing

mortality risk will be accounted for by estimating cause-specific hazard functions. We will apply two analytical approaches: an **on-treatment analysis** (OT) and an **intention to treat analysis** (ITT as per the study by Chan et al.).

Summary of key analysis factors:

- 4 Countries
- 4 DOACs + 1x all DOACS = 5 (warfarin is comparator)
- 2 indications

This brings the number of analyses to $4 * 5 * 2 = 40$ (this number will vary depending on the analytical approach and principal findings).

5.6.3. **Meta-analysis**

Hazard ratios will be reported for each database, exposure and indication separately. Log hazard ratios will also be meta-analysed across databases using a random-effects model using REML (Restricted Maximum Likelihood). 95% Confidence intervals will be provided using the HKSJ method. [12, 13] 95% approximate prediction intervals will be provided. [14] I^2 will be estimated to describe the percentage of the variability in effect estimates that is due to heterogeneity rather than sampling error.

5.6.4. **Missing data**

The analysis will be conducted on the assumption that an individual has a condition or prescription exposure if it is recorded in their electronic health record. No multiple imputation methods will be performed. Therefore, patients with missing records for an indication will be excluded from the analyses.

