5.6.5. **Sample size**

The sample size will be driven by the availability of individuals with exposures and outcomes within each database and no a priori sample size requirement will be stipulated.

5.6.6. **Sensitivity analysis**

If we observe imbalances in propensity score distributions among the cohorts after matching that includes calendar year in the model, we will examine whether undertaking calendar time stratified propensity score matching results in improvement for example by undertaking the propensity score matching within calendar year(s) (such as 2010 to 2014 and 2015 to 2019).

5.7. **Quality control**

The study will be conducted according to the ENCePP code of conduct (European Medicines Agency 2018).

Standard operating procedures or internal process guidance will be adhered to for the conduct of the study. These procedures include rules for secure and confidential data storage, quality-control procedures for all aspects of the study from protocol development to the reporting of the results.

All documents will undergo at least one round a review by an experienced reviewer, while the results from the statistical analysis will be either reviewed or checked via double coding.

The quality control of the data is the responsibility of the data holder.

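### REML pooling of per-database log HRs gives essentially no weight to a database with ILD events in only one arm; sparse contrasts need a likelihood-based estimate alongside it

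*Protocol*

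**What the plan says.** Protocol section 5.1 fixes the design: "Propensity score matched comparative cohort studies with two-stage meta-analysis". Section 5.6.1 sets the first stage, for all analyses: "cause-specific Cox proportional hazards models will be used to estimate the relative hazard ratio of ILD after exposure". Section 5.6.3 sets the second stage: "Log hazard ratios will also be meta-analysed across databases using a random-effects model using REML (Restricted Maximum Likelihood"). It adds "95% Confidence intervals will be provided using the HKSJ method", with prediction intervals and I². It also says "Hazard ratios will be reported for each database, exposure and indication separately".

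Section 5.6.2 plans 1:1 matching within indication and counts 4 databases × 5 exposures × 2 indications = 40 analyses. On numbers, section 5.6.5 says that "no a priori sample size requirement will be stipulated". The only small-sample fallback is a switch from matching to IPTW (5.6.2). No penalised, exact or one-stage estimator is named, and no minimum event count is set for a database to enter the pooling.

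**The concern.** If one matched arm of a database has no ILD event, the Cox partial likelihood is monotone: the log HR runs off to plus or minus infinity and its standard error grows without limit. A model that weights each database by 1/(SE² + τ²) then ignores that database, even though events seen in only one arm say something about the HR.

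Which databases are lost is not random. It depends on which arm has the smaller expected count, so the loss can move the pooled HR as well as cost precision. This would matter most in individual-DOAC or VTE contrasts, if those prove sparse. The protocol makes sparsity plausible. It divides the data into 40 cells, uses a narrow outcome definition (5.5), expects under-ascertainment without hospital linkage (5.8), and draws on databases of very different size (Annex 1). It does not show sparsity. The results are meant to inform PRAC on a safety signal, so a shift in either direction could mislead.

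**Working it through.** The protocol has no sample size, event count or target HR to reproduce. Its one related count, 4 × 5 × 2 = 40, is correct. All event counts, HRs and person-time ratios below are assumptions.

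**1. Weight of a database with one empty arm.** A Cox fit to 3 v 0 events gives SE 12.8, 157 and 661 at 5, 10 and 20 iterations. The weight 1/SE² falls from 1/12.8² = 0.006 to 1/661² = 0.000002. A database with 12 v 8 events has variance 1/12 + 1/8 = 0.208 and weight 4.8.

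**2. Worked data sets** (DOAC, VKA events; equal person-time, so the estimate stratified by database is the ratio of summed counts).
- (12,8), (6,4), (3,0), (2,0): the two retained databases both have HR 1.50, so two-stage = 1.50. All data: 23/12 = 1.92.
- (12,8), (6,4), (0,3), (0,2): two-stage is again 1.50. All data: 18/17 = 1.06.

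The same pooled value comes from opposite evidence. The interval also fails here. The HKSJ variance factor is Σw(y − m)²/(k − 1), and with two identical log HRs it is 0, so the unmodified interval shrinks to a point.

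**3. Which arm is empty.** With μ expected VKA events and equal person-time, P(VKA arm alone empty) = e^(−μ)(1 − e^(−μ·HR)) and P(DOAC arm alone empty) = e^(−μ·HR)(1 − e^(−μ)). For μ = 1 and HR = 2 these are 0.368 × 0.865 = 0.32 and 0.135 × 0.632 = 0.09.

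**4. Simulation.** Four equal-sized databases, Poisson events, log HR = log of the rate ratio, variance 1/e₁ + 1/e₀, databases with an empty arm given no weight, no true heterogeneity. Geometric mean HR, equal person-time:

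| Expected VKA events per database | True HR | Two-stage REML | All databases kept |
|---|---|---|---|
| 1 | 2.0 | 1.41 | 2.08 |
| 2 | 2.0 | 1.74 | 2.09 |
| 3 | 2.0 | 1.87 | 2.07 |
| 5 | 2.0 | 1.96 | 2.03 |
| 2 | 1.5 | 1.33 | 1.53 |
| 2 | 1.0 | 1.00 | 1.01 |
| 2 | 0.67 | 0.79 | 0.65 |

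Most of the shift comes from losing databases. At HR 2, summing counts over the retained databases alone gives 1.43 and 1.80 at 1 and 2 expected events, close to the REML values.

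With DOAC person-time half that of VKA and 2 expected VKA events, true HR 1.0 gives 1.42 v 0.97 and true HR 1.5 gives 1.69 v 1.48, both towards harm. True HR 2.0 shows no shift, because expected events are then equal in the two arms. At 5 expected VKA events, half person-time and true HR 1.0, the result is still 1.11 v 0.98.

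**5. Unequal databases, true HR 2, equal person-time.** Expected VKA events (20,15,5,3) give 1.98 v 2.02; (8,5,2,1) give 1.93 v 2.04; (4,3,1,0.7) give 1.82 v 2.05; (2,1.5,0.5,0.4) give 1.62 v 2.07. In the last case 85% of runs lose a database that has events, and 23% leave fewer than two estimable databases, so there is no meta-analysis. Restricted to runs with at least two, the comparison is 1.61 v 1.88.

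**6. Interval.** Losing databases cuts the HKSJ degrees of freedom from 3. The t multiplier is 3.18 with four databases and 12.71 with two. In most of the sparsest scenarios HKSJ coverage was 0.78 to 0.91, against at least 0.95 for an exact common-HR interval that was also narrower.

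**The case against.** A reader might infer that the method always pulls the pooled HR towards no harm. It does not. There is no shift at true HR 1 with equal person-time, and the shift is towards harm when DOAC person-time is clearly shorter and the true HR is near 1. Section 5.5 ends on-treatment exposure by prescription gaps, so unequal person-time is possible.

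A reader might also infer that the lost databases would be hidden. Section 5.6.3 has HRs reported for each database, exposure and indication, and 5.6.2 plans incidence by group. An empty arm would therefore show as zero incidence and an inestimable HR.

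Nor does the material support replacing REML throughout as the less accurate estimator. At HR 2 and equal person-time, the RMSE of the log HR (two-stage v summed counts) in the four scenarios of step 5 is 0.19 v 0.19, 0.31 v 0.32, 0.42 v 0.46 and 0.57 v 0.62. REML is no worse on total error, and a common-HR model across four health systems is a real assumption.

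It is fair to add that the sparsity is assumed, that individual DOACs are secondary (5.6.1), and that details of zero-event handling often sit in an SAP. The last argument only partly answers the point, because the protocol itself fixes two-stage pooling of Cox log HRs. IPTW may retain more patients, but it cannot give an estimate where an arm still has no events.

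**Conclusion.** The point holds as a conditional weakness of the pooling step. A database with ILD events in only one arm gets essentially no weight. In sparse contrasts this discards information, makes the HKSJ interval very wide or unreliable, and moves the pooled HR in a direction set by which arm is emptier. With similar person-time that is towards 1 if DOACs raise or lower risk. With clearly shorter DOAC person-time and a true HR near 1 it is towards harm.

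At equal person-time the shift is material at 1 to 3 expected VKA events per database, small from about 5 and negligible from about 10. The large AF any-DOAC contrast should be barely affected. These sizes rest on assumed event counts, a constant-rate approximation to Cox and no true heterogeneity. Which contrasts are sparse cannot be told from the protocol; individual-DOAC and VTE contrasts are an assumption. This justifies a cheap addition to the plan, not a change of the main method.

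**What to change.** Keep REML with HKSJ as the main pooling. Add to 5.6.3:

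- For any exposure-by-indication contrast in which a database has no events in one arm (or very few, by a threshold set in advance), the pooled HR is also estimated by a likelihood method that keeps every database with events. One form is the sum of the per-database Cox partial log-likelihood profiles over a grid of log HR, which is the same as a Cox model stratified by database, with a profile-likelihood interval. If IPTW replaces matching, use the weighted likelihoods; the interval then needs a robust adjustment.
- Such contrasts are interpreted from that estimate, with the REML result shown beside it.
- Each forest plot shows events and person-time by arm and database.

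The cost is a few lines of text and a standard model on data that the study already produces. If databases cannot be combined at patient level, only the profile values need to be shared. The downsides should be stated in the protocol. The sparse-data estimate assumes a common HR across databases and does not reduce the RMSE of the point estimate. If one arm has no events in any database, it gives only a one-sided bound. The rule should be fixed before event counts by arm are seen.

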5.8. Limitations of the research methods

Limitations of this study include the potential for missing data if exposure, outcomes, or covariates are not recorded in an individual's electronic health record. Only primary care databases will be used with no linkage to hospital diagnoses that could lead to under ascertainment of outcomes.

Known risk factors for ILD are used as covariates to estimate the propensity score. However, some risk factors will not be possible to include (e.g., environmental exposure) and unknown risk factors may remain. The analysis will control for baseline observed confounders. Complex time-varying analysis of confounders (e.g., drug exposure) will not be performed. Thus, residual confounding remains possible.

Diagnostic coding for ILD is not known to have been validated in the primary care databases available. Although confirmation of the diagnoses requires specialist input, the nature of the diagnosis means that its recording in primary care records could be reasonably accurate. However, this assumption should be treated cautiously. We will assess narrow and broad definitions in the analyses to account for uncertainties around potential misclassification of ILD.

For privacy of the patients, the exact dates of birth and death are not recorded in the used databases. Instead, year of birth is available, and for patients whose death is registered, year of death is available. This increases the estimates for exposure time.

6. Protection of human subjects

Patient confidentiality will be protected according to the EU General Data Protection Regulation (GDPR) on the protection of individuals.

7. Management and reporting of adverse events/adverse reactions

Pursuant to the requirements for reporting of adverse events for secondary data (GVP module VI, VI.C.1.2.1.2), adverse event reporting will not be conducted as part of this study given the study objectives will be met through the use of secondary data.

8. Plans for disseminating and communicating study results

The analysis plan and study results will be published in EUPAS registries upon completion.

9. References

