5.3. Setting and study population

The included study population will consist of adult new users of the anticoagulants of interest (see section on Exposures), as recorded for patients visiting general practices (UK, Germany, Spain, and Italy). Patients will require to have been observed at least once at minimum one year (365 days) prior to entering the cohort. In the UK database, this will be defined as a minimum of 365 days between registration with the practice and the index date. For the other databases, this will be defined as a record of health care system use recorded in the databases at least 365 days prior to the index date.

The population will be stratified by indication for anticoagulation, namely for the management of atrial fibrillation (AF) or for the management of venous thromboembolism (VTE, namely deep vein thrombosis or pulmonary embolism). Indications will be identified by the presence of diagnosis codes within the individual's electronic health record in the year up to the index date. Patients initiating anticoagulation with no diagnostic code for AF or VTE will not be included in the analysis. For patients with multiple indications, the most recent indication (before index date) will be used. Patients with a history of cardiac mechanical valve or mitral stenosis prior to cohort entry will be excluded, as they have an indication for warfarin, not DOACs.

Individuals with a diagnosis of ILD prior to cohort entry (anytime in the patient's prior history) will be excluded from the cohort.

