5.5. Variables

Outcome:

The outcome of interest will consist of an incident diagnosis of ILD. ILD consists of a heterogeneous group of conditions. The ILD phenotype is therefore a composite of different codes representing ILD in general, or as specific conditions that are classed as an ILD. Exclusion of patients with pre-existing ILD will be evaluated using a composite phenotype consisting of any ILD related code. For the outcome in the analysis, a narrower definition of ILD will be used, namely pulmonary fibrosis, pneumonitis, ILD specific codes, and drug induced ILD (please see Appendix for exemplar codes lists). As codes for drug induced ILD are infrequently used, inclusion of this as a specific subgroup may provide limited information. We followed the "narrow" scope list of terms (i.e., very specific preferred terms) documented in the Introductory Guide for Standardised MedDRA Queries (SMQs) Version 25.0 [8]. We mapped these SMQ codes to SNOMED codes and used their OMOP concept IDs, and subsequently removed any codes that indicate another well-defined cause of ILD. Detailed list of codes included are shown in **Annex 2**.

Exposure:

Exposures of interest will consist of VKAs (comparator, consisting of either warfarin, acenocoumarol, phenindione, or phenprocoumon), and DOACs (target, consisting of apixaban, dabigatran, edoxaban and rivaroxaban). Exposures will be identified through prescriptions recorded in the electronic health record. Target exposures will be evaluated by class (any DOAC (direct oral anticoagulants)) and as individual drug substances.

For the on-treatment analysis, patients will be considered continuously exposed from cohort entry (index date) up to 30 days after the date of the last anticoagulant prescription in the patients record. In order to account for different treatment episodes over time, gaps of >90 days between anticoagulant prescriptions will be considered as different treatment episodes and continuous exposure will be censored 30 days after the last prescription before the gap. Detailed list of codes and terms included to identify exposure to DOACs are shown in **Annex 2**.

Other variables:

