Baseline risk factors for ILD will be measured including: age, sex, history of pneumonia, chronic obstructive pulmonary disease, chronic kidney disease, hepatitis C, history of tuberculosis sarcoidosis, history of autoimmune diseases, history of connective tissue disorders, history of sarcoidosis, history of cancer, exposure to medications (nitrofurantoin, sulfonamides, amiodarone, methotrexate, cyclophosphamide, dronedarone, SSRIs/SNRI antidepressants, anticonvulsants, antiplatelets, statins, angiotensin converting enzyme inhibitors (ACEI), angiotensin-II receptor blockers (ARB), thiazide diuretics and systemic fluoroquinolone antibiotics [Detailed list is shown in Annex 2]), smoking status. [9, 10] Smoking status may be missing. We will include current smoking status as a binary variable. An individual will be classed as a current smoker (1) or non-current smoker (0, i.e., other smoking status or the absence of a smoking status) based on the most recent smoking status prior to their index date. Risk factors that will not be reliably identifiable include environment and occupational exposures, family history, and biologics, and will not be considered in the analysis. Information on prior radiotherapy and chemotherapy may not be available for some patients but will be included in the analysis when available.

Additionally, the incidence of ILD has changed substantially over time as well as the prescription patterns of the exposures. We will therefore also account for calendar year in the propensity score analysis.

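### The plan acknowledges under-ascertainment of ILD but not that it may differ between DOAC and VKA users, and has no contact covariate or check designed to show it

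*Protocol*

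**What the plan says.** **Outcome.** Under section 5.6.4 the analysis assumes that "an individual has a condition or prescription exposure if it is recorded in their electronic health record". On the data sources, section 5.8 states: "Only primary care databases will be used with no linkage to hospital diagnoses that could lead to under ascertainment of outcomes". It presents this as a general limitation and does not mention treatment arm.

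**Comparison.** Section 5.5: "Exposures of interest will consist of VKAs (comparator, consisting of either warfarin, acenocoumarol, phenindione, or phenprocoumon), and DOACs" as the target.

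**Adjustment.** Section 5.6.2: "We will include the baseline risk factors and calendar year as predictor variables in the propensity score". The list in section 5.5 begins: "Baseline risk factors for ILD will be measured including: age, sex, history of pneumonia, chronic obstructive pulmonary disease, chronic kidney disease, hepatitis C". It continues with other comorbidities, co-medications and smoking. It contains no count of visits, tests or referrals. Section 5.8 adds: "Complex time-varying analysis of confounders (e.g., drug exposure) will not be performed".

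**Contact before entry.** The only rule on contact is one of eligibility in section 5.3: 365 days of registration in the UK, and elsewhere "a record of health care system use recorded in the databases at least 365 days prior to the index date".

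**Checks.** Section 5.6.6 has one conditional sensitivity analysis, matching within calendar periods, which begins: "If we observe imbalances in propensity score distributions among the cohorts after matching that includes calendar year in the model". Section 5.8 also promises narrow and broad ILD definitions. Section 5.6.2 plans both an on-treatment and an intention-to-treat analysis.

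**The concern.** Under-recording at the same rate in both arms mainly costs precision when the outcome is rare. Under-recording at different rates biases the hazard ratio. The two need different safeguards, and section 5.8 recognises only the first.

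The chance and speed with which ILD is coded plausibly depend on how often a patient is seen. Two routes to a difference between arms should be kept apart:

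- **Before the index date.** Frequency of contact may be related both to the choice of anticoagulant and to the chance of later receiving an ILD code. It is in neither the propensity score nor the SMD check, so an imbalance would go unseen.
- **After the index date.** If VKA treatment brings recurring monitoring contact that DOAC treatment does not, the difference starts with the prescription. Matching on baseline variables cannot remove it.

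The study is to inform the PRAC about a suspected harm. A falsely low hazard ratio would be read as reassurance, so it is the costly error here.

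**Working it through.** The protocol gives no contact rates, detection rates, event numbers or effect size, so there is no stated figure to reproduce. The check has two parts.

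**1. Could any planned element show or remove unequal detection?**

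| Element | Section | Bearing on unequal detection |
|---|---|---|
| Prior record or registration | 5.3 | Sparse and frequent attenders both qualify |
| Propensity score and SMD check | 5.5, 5.6.2 | No contact variable |
| Calendar-time matching | 5.6.6 | Concerns calendar time only, and only if imbalance is seen |
| Narrow and broad ILD lists | 5.8 | Drawn from the same records in both arms |
| On-treatment and intention-to-treat | 5.6.2 | Not designed for this; an indirect signal at best |

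**2. How large could the effect be?** Every input below is an assumption.

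*Unequal completeness of coding.* For a rare outcome, observed HR = true HR × r, where r is the detection probability under DOAC divided by that under VKA.

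| True HR | r = 0.8 | r = 0.9 | r = 1.0 | r = 1.1 |
|---|---|---|---|---|
| 1.0 | 0.80 | 0.90 | 1.00 | 1.10 |
| 1.2 | 0.96 | 1.08 | 1.20 | 1.32 |
| 1.5 | 1.20 | 1.35 | 1.50 | 1.65 |

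With a true HR of 1 and r below 1 the result is apparent protection, so the bias is downwards rather than towards the null.

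*Unequal delay only.* Take an exponential delay to coding with mean d and exponential end of observation with mean F. The share of onsets coded is F/(F + d), so the factor on the HR is (F + d_VKA)/(F + d_DOAC).

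- 3 months (VKA) versus 6 months (DOAC): F = 1 year gives 1.25/1.50 = 0.83; 2 years, 2.25/2.50 = 0.90; 4 years, 4.25/4.50 = 0.94.
- 6 versus 9 months: F = 1 year gives 1.50/1.75 = 0.86; 2 years, 2.50/2.75 = 0.91; 4 years, 4.50/4.75 = 0.95.
- Equal delays give 1.00 at any F.
- Reversed, 6 months (VKA) versus 3 months (DOAC): F = 1 year gives 1.50/1.25 = 1.20; 4 years, 4.50/4.25 = 1.06.

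A second model has fixed follow-up T, a constant onset rate and coded events proportional to T − d(1 − exp(−T/d)). For 3 versus 6 months it gives 0.65 at 0.5 year, 0.75 at 1 year, 0.86 at 2 years and 0.95 at 5 years. Both models show the same pattern: largest with short follow-up, fading with long. Section 5.5 ends on-treatment exposure 30 days after the last prescription, so in that analysis a delayed code can become a missed one.

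*Power.* By the Schoenfeld formula (two-sided 5%, 1:1), 191 events give 80% power for HR 1.5. With the same 191 events, power is 54.5% if 1.5 is seen as 1.35 and 24% if it is seen as 1.20.

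**The case against.** Several stronger readings are tempting, and the document does not support them.

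- **That ILD is found only through routine GP visits.** Annex 1 says that UK practices bring together referral, hospital and test information, that the German database includes specialised practices, and that the Spanish one includes pulmonology and some hospital activity. Section 5.8 says that confirming the diagnosis needs a specialist. This weakens the mechanism. It does not remove it, because a work-up must still be prompted and a code entered.
- **That VKA users are known to be seen more often, so the hazard ratio is biased towards no harm.** The document never mentions INR or monitoring contact. The bias also needs that contact to take place in the contributing practices and to speed or prompt an ILD diagnosis. Neither is documented, so the direction is conditional.
- **That all four databases are biased the same way, so pooling cannot help and a low I² would falsely reassure.** The databases differ in setting and specialist content, and nothing says where monitoring takes place.
- **That nothing planned could give any hint.** Under the delay model the bias shrinks with longer follow-up, so a gap between on-treatment and intention-to-treat results is a weak signal. It is confounded by switching, which only the on-treatment analysis censors.

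It is also fair to say that the sentence in 5.8 is a correct disclosure, that 5.8 admits possible residual confounding, and that negative controls are good practice rather than the correction of a misstatement. These points limit the strength of the concern but leave the omission in place. A separate SAP might add such checks, but this protocol itself specifies the covariates and the sensitivity analysis, and they do not include them.

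**Conclusion.** The concern holds in conditional form. The protocol recognises under-ascertainment but not that it may differ by arm, adjusts for no measure of contact, and plans no check designed to show unequal detection. These facts rest on the text alone.

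The direction and size rest on assumptions. If detection is better under VKA, the hazard ratio is biased downwards: at a detection ratio of 0.9, a true 1.2 appears as 1.08, and at 0.8 as 0.96. With equal detection there is no bias, and at a ratio of 1.1 the same 1.2 appears as 1.32. If the difference is only a 3-month delay, the factor is about 0.83 to 0.86 with mean observation of 1 year and about 0.95 at 4 years. The on-treatment analysis is therefore the more exposed, and long intention-to-treat follow-up the less.

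This is a change the plan should make, held with medium confidence. That the premise is uncertain is itself a reason to measure it.

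**What to change.** 1. **Sections 5.5 and 5.6.2:** add the number of recorded contacts in the 365 days before index to the propensity score and to the SMD check. State that this addresses baseline differences only.
2. **Section 5.6.6:** add prespecified negative-control outcomes, namely conditions not plausibly affected by either drug class that need a consultation to be recorded. Run them in the same matched cohorts with the same Cox models and meta-analysis.
3. **Reporting:** tabulate post-index contact rates per person-year by arm and database. This tests the monitoring premise directly, country by country.
4. **Section 5.8:** state that ascertainment may differ by arm. State also that an ILD hazard ratio near or below 1 will not be read as evidence of no harm if the negative controls or contact rates indicate unequal detection.

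Any calibration of the ILD hazard ratio to the negative controls should be exploratory. ILD needs specialist confirmation and may respond to contact differently from the controls, so calibration could over-correct and inflate a DOAC signal.

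**Cost:** a few extra code lists and some programming on the existing OMOP cohorts, with no new data. Adding the contact count may leave slightly fewer matched pairs.
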